#### 5.1 Inclusion Criteria

A subject must meet the following key criteria in order to be eligible for enrollment in the study:

- 1. Outpatient, male or female of any race, 18 years of age or older.
- 2. Female subjects of childbearing potential must have a negative UPT during Visit 1 (Screening), Visit 2 (if applicable) and practice a reliable method of contraception for the duration of the study.

A female is considered of childbearing potential unless she is:

- postmenopausal for  $\geq 12$  months prior to study treatment administration;
- without a uterus and/or both ovaries; or
- has been surgically sterile for  $\geq 6$  months prior to study treatment administration.

Reliable methods of contraception are:

- hormonal methods (contraceptive pill or implant) or IUD in use  $\geq 90$  days prior to enrolment;
- barrier methods (e.g., diaphragm w/ spermicide or condom w/ spermicide in use  $\geq 14$  days prior to study treatment administration; or
- partner vasectomized  $\geq 3$  months (or confirmed '0' sperm count) prior to enrolment.

[Exception: Females of childbearing potential who are not sexually active are not required to practice a reliable method of contraception. These subjects may be enrolled at Investigator's discretion if they are counseled to remain sexually inactive during the study or agree to use an approved method of contraception should they become sexually active and understand the possible risks in getting pregnant during the study.]

- 3. Moderate to severe glabellar lines (i.e., score of 2 or 3) on maximum frown as assessed by the investigator using the GLS.
- 4. Subject has moderate to severe glabellar lines (i.e., score of 2 or 3) at maximum frown as assessed by the subject using the GLS.
- 5. Able to follow study instructions and likely to complete all required visits.
- 6. Sign the IRB-approved ICF prior to any study-related procedures being performed.

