2.3. Primary Endpoint

The primary effectiveness endpoint will be duration of effect, defined as the number of days from Treatment Day (Baseline) to the day that GLS severity (Investigator assessment) at maximum frown returns to the Baseline value. The treatment will be considered to remain effective for the amount of time during which GLS severity at maximum frown has not returned to Baseline severity. Duration of effect will be estimated by Kaplan–Meier analysis.

Although the trial is not powered for inferential analysis, this will be the most influential outcome in the overall assessment of the effectiveness of prabotulinumtoxinA 40 Units, compared to prabotulinumtoxinA 20 Units, in treating moderate to severe glabellar lines.

Confidential Page 9/58

TABLE 1. SCHEDULE OF EVENTS AND PROCEDURES

Visit Number	V1 ¹ Screening	V2 ¹	V3	V4 (phone f/u)	V5 to V15 ²	V16 ³ (or Final Visit, or ET)	Unscheduled Visit 11
Day/Week/Month	≤ 14D	Tx Day	48Hr	D 7	D30 to D330 Monthly Visits	D365	
Visit Windows				±1 Day	D30 ±3D, ≥D60 ±7D	±14D	
Assessment and Procedures							
Informed Consent	X						
Inc/Excl Criteria	X						
Demographics, Med Hx	X						
Randomization to Study Tx 4		X					
Effectiveness - Investigator							
Glabellar Line Scale ⁵	X	X	X		X	X	X
Global Aesthetic Improvement			X		X	X	X
Effectiveness - Subject							
Glabellar Line Scale ⁵	X	X	X		X	X	X
7-Day Subject Diary		Х —		—			
Global Aesthetic Improvement			X		X	X	X
Subject Satisfaction Score			X		X	X	X
Clinical Interview 6					D30 only	X	X
Safety Evaluations							
Directed Questionnaire ⁷	X		X		X	X	X
Directed Review of Systems	X		X		X	X	X
Vital Signs 8	X		X		X	X	X
Physical Exam 9	X		X		X	X	X
UPT (as applicable)	X	X				X	
Clinical Laboratory Tests 10	X					X	X
ECG	X					X	X
Safety Assessment Phone Call				X			
Brow Area Photography	X	X	X		X	X	X
Concomitant Medications	X	X	X	X	X	X	X
AE Assessment		X	X	X	X	X	X

- 1. Screening and treatment visit can take place the same day, at the discretion of the investigator
- 2. Subjects will be followed monthly until their Glabellar Line Scale score is back to Baseline (Investigator assessment)
- 3. Subject exits study once their Glabellar Line Scale Score has returned to Baseline (Investigator assessment)
- 4. IP may be administered same day as Screening
- 5. Glabellar Line Scale at Maximum Frown, 0=none, 1=mild, 2=moderate, 3=severe
- 6. Clinical Interview Questions
 - What did you like about the treatment (clinically or other feedback)?

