5. STUDY EVALUATIONS

5.1. Effectiveness Assessments

5.1.1. Glabellar Lines Scale (GLS)

The severity of glabellar lines at "maximum frown" will be assessed by both the Investigator (Blinded Evaluator) and subjects using the validated 4-point GLS as per Table 2.

Table 2. GLS at Maximum Frown

Grade	Score	Description
None	0	No lines
Mild	1	Line seen, not sharp
Moderate	2	Line sharper, deep, may see heaping of skin
Severe	3	Deeper line, heaping of skin, skin may be opposed

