7.3. Exploratory Effectiveness Endpoints

Exploratory effectiveness endpoints will be evaluated for signals of effectiveness to explore whether any should be elevated in importance for subsequent trials. These endpoints will be assessed using either logistic regression (for binary endpoints) or survival analysis-type methods as described above. Comparisons will be made between all treatment groups. Chi-square tests of association or Fisher's exact tests will be used to compare treatment group differences in proportion of subjects returning to Baseline at each time point in the study. Exploratory endpoints will be:

Version 1.1 31-May-2023 Confidential Page 18/58

- 1. Duration of effect for GLS responders, defined as the number of days from Treatment Day (Baseline) to the day that GLS severity at maximum frown returns to the Baseline value. Analyses will be conducted for Investigator and subject assessments of GLS. Various responder definitions will be tested (1-Point, 2-Point and 3-Point responders at any time during the study; GLS Score of 0 or 1 at any time during the study; 1-Point responders at Day 30).
- 2. Time to loss of GLS responder status, with responder being defined as a GLS score of 0 or 1 at any point during the study. Analyses will be conducted for Investigator and subject assessments of GLS.
- 3. GLS responder rates (Investigator assessments) at each study visit. Various responder definitions will be tested (1-Point, 2-Point and 3-Point responders; GLS Score of 0 or 1; GLS Score 0 or 1 & ≥2-Point improvement; GLS Score 0 or 1 & ≥2-Point improvement & Investigator GLS = subject GLS).
- 4. GLS responder rates (Subject assessments) at each study visit. Various responder definitions will be tested (1-Point, 2-Point and 3-Point responders; GLS Score of 0 or 1).
- 5. GAIS response (score of 2 or 1) as assessed by Investigator and subject at each visit.
- 6. SSS response (score of 2 or 1) as assessed by subjects at each visit.
- 7. Onset of effect as assessed by subjects through the 7-Day Subject Diary.

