Kaplan-Meier Estimates for Return to B	BL					
1 st Quartile, (95% CI)	x.x(x.x, x.x)	x.x(x.x, x.x)	x.x(x.x, x.x)	x.x(x.x, x.x)	x.x(x.x, x.x)	x.x(x.x, x.x)
Median, (95% CI)	x.x(x.x, x.x)	x.x(x.x, x.x)	x.x(x.x, x.x)	x.x(x.x, x.x)	x.x(x.x, x.x)	x.x(x.x, x.x)
3 rd Quartile, (95% CI)	x.x(x.x, x.x)	x.x(x.x, x.x)	x.x(x.x, x.x)	x.x(x.x, x.x)	x.x(x.x, x.x)	x.x(x.x, x.x)
Adjusted Hazard Ratio (95% CI)	x.xx (x.xx, x.xx)		x.xx (x.xx, x.xx)		x.xx (x.xx, x.xx)	
Stratified Log-Rank p-value	p <x.xxxx< td="">p<x.xxxx< td="">p<x.xxxx< td=""></x.xxxx<>	</x.xxxx<>	</x.xxxx<>		p <x.xxxx< td="">p<x.xxxx< td=""></x.xxxx<>	</x.xxxx<>		p <x.xxxx< td=""></x.xxxx<>	
Unadjusted Hazard Ratio (95% CI)	x.xx (x.xx, x.xx)		x.xx (x.xx, x.xx)		x.xx (x.xx, x.xx)	
Unstratified Log-Rank p-value	p <x.xxxx< td="">p<x.xxxx< td="">p<x.xxxx< td=""></x.xxxx<>	</x.xxxx<>	</x.xxxx<>		p <x.xxxx< td="">p<x.xxxx< td=""></x.xxxx<>	</x.xxxx<>		p <x.xxxx< td=""></x.xxxx<>	

Data for subjects deemed Responder at any point during the study

Duration of effect in days, calculated from Visit 2 (Treatment Day) to when subject returns to Baseline GLS score Responder = At least 2-Point improvement in GLS (max frown)

Version 1.1 31-May-2023 Confidential Page 36/58

Table 14.3.3.1.3 Duration of Effect for GLS Responders (Investigator; 3-Point Responders at any Point During the Study)

GLS (Investigator) Duration of Effect (Return to Baseline GLS score)	PraB 40 (n = xx)	PraB 20 (n = xx)	PraB 40 (n = xx)	OnaB 20 (n = xx)	PraB 20 (n = xx)	OnaB 20 (n = xx)
Subject Status, n (%)						
Returned to BL (event)	xx (xx%)	xx (xx%)	xx (xx%)	xx (xx%)	xx (xx%)	xx (xx%)
Censored	xx (xx%)	xx (xx%)	xx (xx%)	xx (xx%)	xx (xx%)	xx (xx%)
Kaplan-Meier Estimates for Return to B	L					
1 st Quartile, (95% CI)	x.x(x.x, x.x)	x.x(x.x, x.x)	x.x(x.x, x.x)	x.x(x.x, x.x)	x.x(x.x, x.x)	x.x(x.x, x.x)
Median, (95% CI)	x.x(x.x, x.x)	x.x(x.x, x.x)	x.x(x.x, x.x)	x.x(x.x, x.x)	x.x(x.x, x.x)	x.x(x.x, x.x)
3 rd Quartile, (95% CI)	x.x(x.x, x.x)	x.x(x.x, x.x)	x.x(x.x, x.x)	x.x(x.x, x.x)	x.x(x.x, x.x)	x.x(x.x, x.x)
Adjusted Hazard Ratio (95% CI)	x.xx (x.xx,	x.xx)	x.xx (x.xx	x.xx (x.xx, x.xx)		x.xx)

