Stratified Log-Rank p-value	p <x.xx< td="">xx	p<x.xxxx< td="">p<x.xxxx< td=""></x.xxxx<>	</x.xxxx<>	</x.xx<>	xx	p <x.xxxx< td="">p<x.xxxx< td=""></x.xxxx<>	</x.xxxx<>		p <x.xxxx< td=""></x.xxxx<>	
Unadjusted Hazard Ratio (95% CI)	x.xx (x.xx,	x.xx)	x.xx (x.xx, x.xx)		x.xx (x.xx, x.xx)	
Unstratified Log-Rank p-value	p <x.xx< td="">xx	p<x.xx< td="">xx	p<x.xxxx< td=""></x.xxxx<>	</x.xx<>	</x.xx<>	xx	p <x.xx< td="">xx	p<x.xxxx< td=""></x.xxxx<>	</x.xx<>	xx	p <x.xxxx< td=""></x.xxxx<>	

Data for subjects deemed Responder at any point during the study

Duration of effect in days, calculated from Visit 2 (Treatment Day) to when subject returns to Baseline GLS score Responder = At least 3-Point improvement in GLS (max frown)

Version 1.1 31-May-2023 Confidential Page 37/58

Table 14.3.3.1.4 Duration of Effect for GLS Responders (Investigator; GLS Score of 0 or 1 at any Point During the Study)

		`	0 /		·	• • • • • • • • • • • • • • • • • • • •
GLS (Investigator) Duration of Effect (Return to Baseline GLS score)	PraB 40 (n = xx)	PraB 20 (n = xx)	PraB 40 (n = xx)	OnaB 20 (n = xx)	PraB 20 (n = xx)	OnaB 20 (n = xx)
Subject Status, n (%)						
Returned to BL (event)	xx (xx%)	xx (xx%)	xx (xx%)	xx (xx%)	xx (xx%)	xx (xx%)
Censored	xx (xx%)	xx (xx%)	xx (xx%)	xx (xx%)	xx (xx%)	xx (xx%)
Kaplan-Meier Estimates for Return to B	L					
1 st Quartile, (95% CI)	x.x(x.x, x.x)	x.x(x.x, x.x)	x.x (x.x, x.x)	x.x(x.x, x.x)	x.x(x.x, x.x)	x.x(x.x, x.x)
Median, (95% CI)	x.x(x.x, x.x)	x.x(x.x, x.x)	x.x (x.x, x.x)	x.x(x.x, x.x)	x.x(x.x, x.x)	x.x(x.x, x.x)
3 rd Quartile, (95% CI)	x.x(x.x, x.x)	x.x(x.x, x.x)	x.x (x.x, x.x)	x.x(x.x, x.x)	x.x(x.x, x.x)	x.x(x.x, x.x)
Adjusted Hazard Ratio (95% CI)	x.xx (x.xx,	, x.xx)	x.xx (x.xx	x.xx (x.xx, x.xx)		x.xx)
Stratified Log-Rank p-value	p <x.xx< td="">xx	p<x.xx< td="">XX	p<x.xxxx< td=""></x.xxxx<>	</x.xx<>	</x.xx<>	xx	p <x.xx< td="">XX	p<x.xxxx< td=""></x.xxxx<>	</x.xx<>	XX	p <x.xxxx< td=""></x.xxxx<>	
Unadjusted Hazard Ratio (95% CI)	x.xx (x.xx,	, x.xx)	x.xx (x.xx, x.xx)		x.xx (x.xx, x.xx)	

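### The ≥3-point GLS responder rate counts Baseline-moderate subjects who cannot reach it, so it is capped at the severe share and its comparison is modestly weakened

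*SAP*

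**What the plan says.** The scale has four grades: "Glabellar Line Scale at Maximum Frown, 0=none, 1=mild, 2=moderate, 3=severe" (SAP Table 1, footnote 5). Entry is limited at both ratings. Protocol 5.1 item 3 requires "Moderate to severe glabellar lines (i.e., score of 2 or 3) on maximum frown as assessed by the investigator using the GLS", and item 4 requires "Subject has moderate to severe glabellar lines (i.e., score of 2 or 3) at maximum frown as assessed by the subject using the GLS".

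SAP 7.3 item 3 lists the investigator responder-rate definitions: "1-Point, 2-Point and 3-Point responders; GLS Score of 0 or 1; GLS Score 0 or 1 & ≥2-Point improvement", followed by a sixth that adds agreement between the investigator and subject scores. Item 4 lists the 1-, 2- and 3-point definitions and a score of 0 or 1 for the subject rating. The point thresholds are minimums. The footnote to Table 14.3.3.1.2 reads "Responder = At least 2-Point improvement in GLS (max frown" and that to Table 14.3.3.1.3 reads "Responder = At least 3-Point improvement in GLS (max frown".

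Tables 14.3.3.3.1 (investigator) and 14.3.3.3.2 (subject) give each definition a percentage with confidence interval, odds ratios and p-values for the three pairwise comparisons, under a single N per arm and visit. SAP 7.7 bases percentages on the relevant analysis population in each arm. Neither document restricts the 3-point rate to subjects who were severe at Baseline. Randomization is stratified by Baseline GLS, moderate versus severe (Protocol 6.2, SAP 3.2).

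**The concern.** A Baseline-moderate subject has only two points to lose. Such a subject contributes nothing to the numerator of the ≥3-point rate but counts in its denominator. The printed rate therefore mixes the response among severe subjects with the proportion who were severe, and it sits in the same table as the ≥1-point and ≥2-point rates, which have no such ceiling. SAP 7.3 uses these endpoints to explore which might be given more weight in later trials, so a reader will compare the rows with one another. A capped rate with a slightly attenuated odds ratio is at a disadvantage in that comparison for reasons unrelated to treatment.

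There is also an overlap among the definitions: one row presented as a composite may add nothing to the row above it.

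**Working it through.** **Inputs.** Scale 0 to 3 (SAP Tables 1 and 2). Baseline 2 or 3 for each rater (Protocol 5.1 items 3 and 4). Improvement = Baseline score b minus visit score s. 50 subjects per arm (SAP 7.6). The documents give neither the share severe at Baseline, f, nor the ≥3-point rate among severe subjects, r. Both are assumed below and f is shown as a range. There is no planned figure for this endpoint to reproduce.

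**Step 1: which changes qualify.**

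| Baseline | Visit score | Improvement | ≥2-point | ≥3-point | 0/1 and ≥2-point |
|---|---|---|---|---|---|
| 2 | 0 | 2 | yes | no | yes |
| 2 | 1 | 1 | no | no | no |
| 2 | 2 | 0 | no | no | no |
| 2 | 3 | −1 | no | no | no |
| 3 | 0 | 3 | yes | yes | yes |
| 3 | 1 | 2 | yes | no | yes |
| 3 | 2 | 1 | no | no | no |
| 3 | 3 | 0 | no | no | no |

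The ≥3-point response occurs in one cell, 3 to 0, and in none of the four Baseline-2 cells.

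**Step 2: the ceiling.** All-subject rate = f × r + (1 − f) × 0 = f × r, which cannot exceed f. With r = 40%, the table would show 10%, 20% or 30% at f = 25%, 50% or 75%.

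**Step 3: the unadjusted odds ratio.** Assume r = 40% and 20% in two arms with the same f. Among severe subjects, OR = (0.40/0.60)/(0.20/0.80) = 2.67.

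| Moderate share (1 − f) | All-subject rates | Risk ratio | Odds ratio |
|---|---|---|---|
| 20% | 32% vs 16% | 2.0 | (0.32/0.68)/(0.16/0.84) = 2.47 |
| 40% | 24% vs 12% | 2.0 | (0.24/0.76)/(0.12/0.88) = 2.32 |
| 50% | 20% vs 10% | 2.0 | (0.20/0.80)/(0.10/0.90) = 2.25 |

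The risk ratio does not move, because f cancels. As f falls the odds ratio approaches that risk ratio of 2.0, not 1.

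**Step 4: precision.** Normal-approximation power for two proportions, two-sided 0.05, same assumed rates: Φ[(d − 1.96 × se0)/se1], where d is the difference, se0 uses the pooled rate and se1 the separate rates. At f = 50%:

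- All subjects, n = 50 per arm, 10% vs 20%: se0 = √(0.15 × 0.85 × 2/50) = 0.0714; se1 = √[(0.09 + 0.16)/50] = 0.0707; power = Φ[(0.10 − 0.140)/0.0707] = 0.286.
- Severe only, n = 25 per arm, 20% vs 40%: se0 = √(0.30 × 0.70 × 2/25) = 0.1296; se1 = √[(0.16 + 0.24)/25] = 0.1265; power = Φ[(0.20 − 0.254)/0.1265] = 0.335.

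At f = 25% the pair is 0.155 and 0.187; at f = 75% it is 0.434 and 0.471. Under these assumptions, dropping the moderate subjects raises power slightly despite the smaller N.

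**Step 5: the overlapping row.** A ≥2-point gain means s ≤ b − 2, and b is at most 3, so s ≤ 1. The added condition of a score of 0 or 1 is always met, and the two definitions agree in all eight cells of Step 1. By the same argument the sixth definition reduces to a ≥2-point gain with equal investigator and subject scores. That one is a distinct rule. The redundant row would repeat at 13 in-person post-treatment visits (V3 and V5 to V16), or 13 × 3 = 39 repeated pairwise comparisons.

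**The case against.** The case for leaving the rate alone has substance. The mITT population is the stated population for exploratory endpoints (SAP 7.5.1), and Protocol 12.4 items 4 and 5 define the 3-point rate with no severity restriction. The share of all treated subjects who gain three points is a legitimate descriptive quantity. Table 14.2.1.1 reports moderate and severe counts by arm, so an alert reader can see the ceiling. That argues for keeping the all-subject percentage available. It does not argue for basing the odds ratio and p-value on it.

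Two stronger readings are tempting, and the documents do not support them. A reader might infer that the ≥3-point rate reflects enrolment mix and not the drug. It is f × r, and r is the drug response among severe subjects; in Step 3 the risk ratio is unchanged and the odds ratio moves only modestly. A reader might also infer that the arms are compared unfairly. Randomization is stratified by Baseline GLS, so no between-arm bias from case mix is expected. The stratification text does not name the rater, so balance on the subject-rated Baseline is less tightly controlled, but chance imbalance is not expected bias.

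The odds-ratio attenuation also presumes an unadjusted model. SAP 7.3 specifies logistic regression without listing covariates. If Baseline GLS were entered, as in the primary model in SAP 7.1, the problem would change form: the moderate group has no ≥3-point events, so its coefficient could not be estimated (separation).

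On the overlapping row, a reader might take it as a stricter definition confirming the ≥2-point result. It will show identical numbers in the same table, and no alpha is allocated across these endpoints, so the harm is small.

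**Conclusion.** The ceiling and the row identity are exact consequences of the scale and the entry criteria and need no assumption. The size of the ceiling's effect does rest on assumptions, because the documents give neither the severity mix nor the expected 3-point rates. With severe-subject rates of 40% and 20%, an unadjusted odds ratio of 2.67 becomes 2.47 to 2.25 at 20% to 50% moderate, and power at 50 per arm is lower by roughly 0.03 to 0.05 than in severe subjects alone for severe shares of 25% to 75%. This is a minor weakness in exploratory rows. It leaves the primary endpoint untouched. The 3-point duration tables (14.3.3.1.3 and 14.3.3.2.3) already contain only subjects who were severe at Baseline, so their results would not change.

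**What to change.** In SAP 7.3 items 3 and 4 and Tables 14.3.3.3.1 and 14.3.3.3.2, base the ≥3-point percentage, odds ratio and p-value on subjects whose Baseline GLS by the same rater is 3, and print that N. Leave that Baseline GLS out of any model for these rows, since it is constant there. The all-subject mITT percentage may stay as a descriptive line, footnoted to say that it cannot exceed the share severe at Baseline.

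Editorially, drop the row requiring a score of 0 or 1 plus a ≥2-point gain, or footnote it as identical to the ≥2-point row, and restate the sixth definition as a ≥2-point gain with equal investigator and subject scores.

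The cost is a subset flag, a few lines of SAP text and a smaller displayed N. No data collection changes, and the subjects left out of the comparison could not have met the definition.

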#### Phase III U.S. Based Clinical Trials

The two identical U.S. Phase III studies, EV-001 and EV-002, enrolled subjects who were selected from a population of healthy adults, at least 18 years of age, who had moderate to severe glabellar lines at maximum frown (REF 2). Eligible subjects were randomly assigned in a 3:1 ratio to receive a single treatment of either prabotulinumtoxinA or placebo. Subjects were followed for 150 days.

The primary efficacy endpoint was defined as the proportion of subjects classified as responders on Day 30. This was a composite endpoint in which a responder was a subject with a 2-point improvement or greater on the GLS from Day 0 to Day 30 at maximum frown, only if independently agreed by both investigator and subject assessment.

Both studies met the primary endpoint of superiority over placebo. The percentages of responders in the intent to treat population for the composite primary endpoint, a two point or greater score

composite improvement, in each of the two controlled single dose studies were:

- EV-001: 1.2% placebo, 67.5% prabotulinumtoxinA, with an absolute difference between the groups of 66.3%, 95% CI (59.0, 72.4).
- EV-002: 1.3% placebo, 70.4% prabotulinumtoxinA, with an absolute difference between the groups of 69.1%, 95% CI (61.5, 75.1).

In the **EV-001 study**, analysis of the secondary endpoints investigated the response at maximum frown beyond Day 30 using a two-point composite score. A subject was considered a responder only if a  $\geq 2$  point improvement had occurred on the GLS at maximum frown from Day 0, by both investigator and subject assessment:

- At Day 90 (post hoc), the percentage of responders was 1.3% in the placebo group and 26.5% in the prabotulinumtoxinA group with an absolute difference of 25.2%, p<0.001.
- At Day 120, the percentage of responders was 1.3% in the placebo group and 8.3% in the prabotulinumtoxinA group with an absolute difference of 7.0%, p=0.023.
- At Day 150 or early termination, the percentage of responders was 0.0% in the placebo group and 4.6% in the prabotulinumtoxinA group. The absolute difference of 4.6% between the groups remained statistically significant for the composite endpoint, p=0.041.

The 2-point composite score results were similar in the EV-002 study to the EV-001 study for the secondary endpoints:

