#### **10.3** Effectiveness Assessments

#### 10.3.1 Glabellar Lines Scale (GLS)

The severity of glabellar lines at "maximum frown" will be assessed by both the Investigator (Blinded Evaluator) and subjects using the validated 4-point GLS as per Table 2 and in Appendix C. The accompanying photonumeric guidance will be provided separate from this protocol.

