14.3.3.3 GLS Responder Rates

Table 14.3.3.3.1 GLS Responder Rates (Investigator)

GLS Responder Rate	Pı	raB 40 Pr	aB 20	OnaB 20		P-value / OR	
Investigator	(n	= xx) (n	= xx)	$(\mathbf{n} = \mathbf{x}\mathbf{x})$	PraB-40 vs. PraB-20	PraB-40 vs. OnaB-20	PraB-20 vs. OnaB-20
V3 (48hrs)	N	XX	XX	XX			
≥1-Point	Percent, CI 95%	xx.x% [xx.x, xx.x]	xx.x% [xx.x, xx.x]] xx.x% [xx.x, xx.x]	x.xxxx	X.XXXX	X.XXXX
	OR (95% CI)				x.xxxx (xx.x, xx.x	x) x.xxxx (xx.x, xx.x)	x.xxxx (xx.x, xx.x)
	OR (p-value)				X.XXXX	X.XXXX	X.XXXX
≥2-Point	Percent, CI 95%	xx.x% [xx.x, xx.x]	xx.x% [xx.x, xx.x]] xx.x% [xx.x, xx.x]	X.XXXX	X.XXXX	X.XXXX
	OR (95% CI)				x.xxxx (xx.x, xx.x	x) x.xxxx (xx.x, xx.x)	x.xxxx (xx.x, xx.x)
	OR (p-value)				X.XXXX	X.XXXX	X.XXXX
≥3-Point	Percent, CI 95%	xx.x% [xx.x, xx.x]	xx.x% [xx.x, xx.x]] xx.x% [xx.x, xx.x]	X.XXXX	X.XXXX	X.XXXX
	OR (95% CI)				x.xxxx (xx.x, xx.x	x) x.xxxx (xx.x, xx.x)	x.xxxx (xx.x, xx.x)
	OR (p-value)				X.XXXX	X.XXXX	X.XXXX
Score 0 or 1	Percent, CI 95%	xx.x% [xx.x, xx.x]	xx.x% [xx.x, xx.x]] xx.x% [xx.x, xx.x]	X.XXXX	X.XXXX	X.XXXX
	OR (95% CI)				x.xxxx (xx.x, xx.x	x) x.xxxx (xx.x, xx.x)	x.xxxx(xx.x, xx.x)
	OR (p-value)				X.XXXX	X.XXXX	X.XXXX
Score 0 or 1 & \geq 2-Point	Percent, CI 95%	xx.x% [xx.x, xx.x]	xx.x% [xx.x, xx.x]] xx.x% [xx.x, xx.x]	X.XXXX	X.XXXX	X.XXXX
improvement	OR (95% CI)				x.xxxx (xx.x, xx.x	x) x.xxxx (xx.x, xx.x)	x.xxxx(xx.x, xx.x)
	OR (p-value)				X.XXXX	X.XXXX	X.XXXX
Score 0 or 1 & \geq 2-Point	Percent, CI 95%	xx.x% [$xx.x$, $xx.x$]	xx.x% [$xx.x$, $xx.x$]	xx.x% [xx.x, xx.x]	X.XXXX	X.XXXX	X.XXXX
improvement & Inv.	OR (95% CI)				x.xxxx (xx.x, xx.x	x) x.xxxx (xx.x, xx.x)	x.xxxx(xx.x, xx.x)
GLS = subject GLS	OR (p-value)				X.XXXX	X.XXXX	X.XXXX
	N	XX	XX	XX			
≥1-Point	Percent, CI 95%	xx.x% [$xx.x$, $xx.x$]	xx.x% [xx.x, xx.x]	xx.x% [xx.x, xx.x]	X.XXXX	X.XXXX	X.XXXX
	OR (95% CI)				x.xxxx (xx.x, xx.x	x) x.xxxx (xx.x, xx.x)	x.xxxx(xx.x, xx.x)
	OR (p-value)				X.XXXX	X.XXXX	X.XXXX
≥2-Point	Percent, CI 95%	xx.x% [$xx.x$, $xx.x$]	xx.x% [xx.x, xx.x]	xx.x% [xx.x, xx.x]	X.XXXX	X.XXXX	X.XXXX
	OR (95% CI)				x.xxxx (xx.x, xx.x	x) x.xxxx (xx.x, xx.x)	x.xxxx(xx.x, xx.x)
	OR (p-value)				X.XXXX	X.XXXX	X.XXXX
≥3-Point	Percent, CI 95%	xx.x% [$xx.x$, $xx.x$]	xx.x% [xx.x, xx.x]	xx.x% [xx.x, xx.x]		X.XXXX	X.XXXX
	OR (95% CI)				x.xxxx (xx.x, xx.x	x) x.xxxx (xx.x, xx.x)	x.xxxx(xx.x, xx.x)
1	OR (p-value)				X.XXXX	X.XXXX	X.XXXX
	Percent, CI 95%	xx.x% [xx.x, xx.x]	xx.x% [xx.x, xx.x]] xx.x% [xx.x, xx.x]	X.XXXX	X.XXXX	X.XXXX

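### One exploratory GLS responder definition in SAP 7.3 requires identical Investigator and subject scores, not a response found by both raters

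*SAP*

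**What the plan says.** SAP section 7.3, item 3, is headed "GLS responder rates (Investigator assessments) at each study visit" and lists six responder definitions. The last is "GLS Score 0 or 1 & ≥2-Point improvement & Investigator GLS = subject GLS". The corresponding row of Table 14.3.3.3.1 carries the same condition ("GLS = subject GLS"), so a programmer working from either the text or the shell would code equality of the two scores. Item 4 and Table 14.3.3.3.2 define response on the subject's rating alone, and the other five definitions in item 3 use the Investigator's rating alone.

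Both raters use the same 0–3 scale: the GLS is "assessed by both the Investigator (Blinded Evaluator) and subjects using the validated 4-point GLS" (protocol 10.3.1). Protocol 5.1 sets two separate entry criteria, "Moderate to severe glabellar lines (i.e., score of 2 or 3) on maximum frown as assessed by the investigator using the GLS" and "Subject has moderate to severe glabellar lines (i.e., score of 2 or 3) at maximum frown as assessed by the subject". Nothing requires the two Baseline scores to match.

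For the two earlier U.S. Phase III studies, protocol section 1.1 describes a dual-rater response: at least a 2-point GLS improvement, counted "only if independently agreed by both investigator and subject assessment".

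**The concern.** A condition that brings in the second rater would ordinarily confirm that the subject also sees a response. Equality of scores does not do that. It fails a subject when one rater gives 0 and the other 1, even though both ratings are responses. It also ignores the subject's own Baseline, so a matching visit score can pass although the subject's rating moved by only one point.

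Item 3 is analysed between all treatment groups, with odds ratios, confidence intervals and p-values in the table. These endpoints are meant to show what deserves a higher place in later trials. A definition that changes classification whenever raters split between 0 and 1 could distort that signal in either direction. No other definition in items 3 or 4 supplies the rate at which both raters find a response, so the reader has no correct version beside it.

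**Working it through.** The documents state no figure for this definition, so there is nothing to reproduce. The check is a full enumeration.

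**Inputs.** Investigator Baseline BI and subject Baseline BS are each 2 or 3 (protocol 5.1). Visit scores I and S each run from 0 to 3 (protocol 10.3.1). That gives 2 × 2 × 4 × 4 = 64 patterns, written (BI, BS, I, S).

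**Rules.**
- SAP rule, read literally under its Investigator heading: I ≤ 1, BI − I ≥ 2, and I = S.
- Dual response: I ≤ 1, BI − I ≥ 2, S ≤ 1, BS − S ≥ 2.

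From a Baseline of 2 or 3, a 2-point gain always ends at 0 or 1. The score condition therefore adds nothing, and what separates the two rules is the equality clause.

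**Result by Baseline pair (visit scores I, S).**

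| BI/BS | Dual response | SAP rule | Wrongly rejected | Wrongly accepted |
|---|---|---|---|---|
| 2/2 | (0,0) | (0,0) | none | none |
| 2/3 | (0,0), (0,1) | (0,0) | (0,1) | none |
| 3/2 | (0,0), (1,0) | (0,0), (1,1) | (1,0) | (1,1) |
| 3/3 | (0,0), (0,1), (1,0), (1,1) | (0,0), (1,1) | (0,1), (1,0) | none |
| Patterns | 1+2+2+4 = 9 | 1+1+2+2 = 6 | 4 | 1 |

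Five patterns are common to both rules. The rejected dual responses are (3,3,0,1), (3,3,1,0), (3,2,1,0) and (2,3,0,1). The accepted pattern that is not a dual response is (3,2,1,1): the Investigator improves by 2 and the subject by 2 − 1 = 1.

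**Perverse direction.** (3,3,1,1) is a success. If the subject's rating is better, (3,3,1,0), it becomes a failure. If the Investigator's rating is better, (3,3,0,1), it also becomes a failure.

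**Alternative reading.** Suppose the 2-point condition is applied to both raters as well as the equality. Then (3,2,1,1) drops out and 5 patterns qualify, but the same 4 of 9 dual responses are still rejected.

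**Net effect.** Write P(i,s) for the visit-score probabilities within a Baseline pair. SAP rate minus dual-response rate is:
- 2/2: 0
- 2/3: −P(0,1)
- 3/3: −[P(0,1) + P(1,0)]
- 3/2: P(1,1) − P(1,0), which is positive whenever both raters giving 1 is commoner than Investigator 1 with subject 0.

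**Illustrations, by assumption only.**
- Among dual responders at 3/3, let each rater independently give 0 with probability q and otherwise 1. The share rejected is 2q(1 − q): 18% at q = 0.1, 32% at q = 0.2, 50% at q = 0.5. With perfect agreement it is 0%.
- Assume bivariate-normal ratings with 20% score 0 and 60% score 1 for each rater, correlation 0.7, and the same visit distribution in every Baseline pair. Dual response versus SAP rule is then 71% v 54% at 3/3, 11% v 11% at 2/2, 20% v 11% at 2/3 and 20% v 54% at 3/2.
- Assume instead 10% score 0 and 70% score 1. The loss at 3/3 is about 13 points at correlation 0.5 and about 6 points at 0.9.

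**The case against.** The strongest reply is that the SAP does not call this row a composite and does not say it should reproduce the earlier Phase III definition, which the protocol gives only as background. It is the last of several definitions to be tried, and it can be read as a deliberately strict one: an Investigator response confirmed by an identical subject score. This stands as far as intent goes, since the purpose of the equality is not documented. It does not rescue the row as a responder rate. A stricter response rule should not turn a success into a failure because a rating got better, nor accept a one-point subject change while rejecting two 2-point changes. If concordance was the aim, it should be labelled as concordance.

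It is also fair that the reach is small. Investigator and subject 2-point rates are reported separately at every visit, both scores are collected at the same visits, and the dual-response rate can be derived later without new data.

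Three stronger inferences are tempting and not supported:
- A reader might infer that the rate is deflated overall. At 2/2 there is no change and at 3/2 there may be inflation, so the net direction depends on a Baseline mix that the documents do not give.
- A reader might put a single figure on the loss. That needs the joint distribution of the two ratings. The illustrations move widely with assumed values, and those for 3/3 alone show only the pair most exposed to loss.
- A reader might object that the result cannot be set against the 67.5% and 70.4% composite rates in protocol section 1.1. Neither document plans that comparison; the planned comparisons are between the three treatment groups.

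**Conclusion.** The point holds as a definitional error in one exploratory row. Followed as written, the rule rejects 4 of the 9 dual-response patterns and accepts 1 pattern in which the subject improved by only one point. These counts follow from the literal text and the entry criteria and need no distributional assumption. Calling them misclassifications assumes that the row is meant to show response confirmed by both raters. The dual-rater response in protocol section 1.1 makes that plausible, but the SAP does not state it. How many subjects are affected cannot be determined from the documents. The primary and secondary endpoints are untouched, so this is a minor correction worth making because it is nearly free.

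**What to change.** In SAP 7.3, item 3, replace the equality condition. A responder has a GLS score of 0 or 1 and at least a 2-point improvement from own Baseline on the Investigator assessment and, independently, on the subject assessment at the same visit. Change the matching row of Table 14.3.3.3.1. This corrects all five misclassified patterns and agrees with the dual-rater response described in protocol section 1.1. If exact agreement between the two scores is of interest, report it in its own row as a concordance measure and not as a responder rate.

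The cost is one phrase and one table row. Both ratings are already scheduled at the same visits, so no data collection changes. The edit should be made before database lock, the point by which the SAP says its methods are to be fixed.
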